7.2 Recruitment

Subjects will be recruited through the NIH Normal Volunteer Office, by word of mouth and through local advertisement (IRB approved flyers, newsletters, websites).

7.3 Screening Methods

7.3.1 Pre-screening

The NIH Patient Recruitment and Public Liaison Office will receive inquiries from interested study subjects. Pre-screening by this office will exclude patients who cannot regularly attend the NIH Metabolic Unit to acquire study foods, and those with significant claustrophobia that will preclude the imaging tests that are required to participate in the full protocol. All others will be contacted by the protocol team to review exclusion criteria. Eligible subjects will be invited to Clinical Research Center for a screening visit.

7.3.2 Screening visit (Baseline Phase Visit 1)

Patients will be invited to come to the OP-9 (Outpatient 9) Multiple Medical Specialties Clinic to obtain informed consent by a member of the investigative team. A limited physical exam with current weight and evaluation of venous access will be performed. A thorough medication history will be obtained with special attention given to drugs that may confound the interpretation of metabolic testing such as psychotropic agents, antiretroviral agents, sympathomimetic amines or beta blockers. An

electrocardiogram and baseline blood work (electrolytes, chronic liver disease work-up, renal function, vitamins, thyroid function, HgbA1C, HIV test), a serum pregnancy test and a urine test to screen for illicit drugs will be obtained. Instructions for completing detailed 7-day food records will be given to participants by a member of the Nutrition Dept staff.

7.4 Study Design

We anticipate that 84 subjects will need to complete the baseline phase and be randomized, with an anticipated dropout of about 20 subjects during the diet phase, in order for 64 subjects to complete the 12-week diet phase. Based on previous NIH Clinical Center dietary protocols with a similar baseline phase, we anticipate that 30 to 55% of enrolled subjects will not complete the baseline phase due to lack of attendance, non-compliance with 7-day food records, and/or discovery of an underlying exclusionary condition during the baseline phase history, physical examination or laboratory testing. Therefore, *up to* 180 subjects will be enrolled in the baseline phase so that a sufficient number of subjects (64) will complete the diet phase.

After completing the baseline phase, 84 subjects will be randomized to 1 of 3 diets (Table 3), to be maintained for 12 consecutive weeks. We anticipate that about 20% of subjects will dropout during the diet phase. Therefore 64 subjects are expected to complete the diet phase.

Table 3: Fatty Acids in 3 Study Diets

Diet Group	omega-6 LA*	omega-3 ALA	omega-6 AA	omega-3 HUFA	%omega-6 in HUFA**
A. Orange	8.00	0.40	0.045	0.045	80
B. Blue	1.00	0.40	0.045	0.045	50
C. Green	1.00	0.40	0.045	0.81	20

*Fatty acid intake as percentages of daily food energy (en%).

** Predicted percentage of omega-6 HUFA in total omega-6 and omega-3 HUFA, via the Lands empirical equation, as detailed in Appendix 2

Please see Section 7.1: Study overview and design and Appendix 1: Study Design Flow Diagram.

7.5 Study Procedures

The main study lasts 16 weeks and is divided into 2 phases: 1) a 4 week ‘baseline phase’, and 2) a 12 week ‘diet phase’. There is also an optional 36 week ‘continuation phase’ for participants receiving diet ‘B’.

During the 4 week baseline phase participants will visit the NIH outpatient clinics three times as shown in Table 3 below. Visit 1 is a screening visit lasting about 1 hour. During Visit 2 laboratory tests will be reviewed, and participants will fill out questionnaires, which will take about 2 hours. At Visit 3, participants will receive about 6 hours of testing and will be randomly assigned to 1 of 3 study diets.

During the 12 week diet phase participants will eat only the study foods that are supplied by the NIH metabolic kitchen. They will visit the NIH outpatient metabolic unit every morning for breakfast (Monday-Friday) for all 12 weeks of the diet phase. Each of these 60 visits will last about 20 minutes, for a total of 20 hours. They will fill out the Comprehensive Psychopathological Rating Scale-Self-Affective (CPRS) questionnaire (see Section 7.6.6) after breakfast once every 2 weeks, which takes about 10

minutes to complete. Once every 4 weeks after breakfast, on Diet Day 28 and 56, they will have additional testing for about 1.5 hours; on Diet Day 84 they will have additional testing for about 6 hours as shown in Table 4 below. During the optional 9 month (36 week) continuation phase participants continue to eat only the study foods supplied by the metabolic kitchen. They will continue to visit the NIH outpatient metabolic unit every morning for breakfast (Monday-Friday) for all 36 weeks of the continuation phase. Each of these 180 visits will last about 20 minutes, for a total of 60 hours. Participants will fill out the CPRS questionnaire after breakfast once every 2 weeks, which requires about 10 minutes to complete. Once every 6 weeks after breakfast, participants will undergo additional testing for 3 to 6 hours as shown in Table 5 below.

All study procedures are for research purposes only.

Baseline Phase

The sequence of procedures in the baseline phase is given in Table 4. All time-points are targets, and may be adjusted based on practical considerations.

Table 4: Procedures during the Baseline Phase

Baseline Phase Testing Visits (4 week phase, Days 1-28)

Procedure	Visit 1 (Day 1)	Visit 2 (Day 14)	Visit 3 (Day 21-28)
Blood Draw	▲		▲
Saliva DNA testing	▲		
Urine Drug Screen	▲		
Urine Laboratory Testing	▲		▲
7-day Food Records	▲	▲	
Medical Exam and Interview	▲	▲	
Eating Questionnaires		▲	
Mood Questionnaires		▲	
Weight, Anthropometrics and Vital Signs	▲	▲	▲
Electrocardiogram (EKG)	▲		
DEXA Scan			▲
Muscle and Adipose Tissue Biopsies			▲
Buffet Meal Test			▲

Baseline phase: 1st Visit

The first visit of the baseline phase is described in detail in Section 7.3.2 Screening Visit.

Baseline phase: 2nd Visit

Participants will return for an outpatient visit about 14 days after Baseline Visit 1. The 7-day food records and the results of the laboratory testing will be reviewed. Questionnaires to evaluate eating, satiety and mood will be administered (see Section 7.6.6). Those who remain eligible will be scheduled for a 3rd baseline visit.

Baseline phase: 3rd Visit

Participants will return for an outpatient visit about 7 to 14 days after the 2nd Visit. If their weight is stable, participants will have additional tests, which will require about 6 hours (Testing procedures are listed in Table 4).

Participants will receive a schedule for the remaining study visits and tests. Participants will then be randomized to 1 of 3 diets as described in Section 7.6.2.

Study Diets

The 3 study diets differ only in the amounts of fatty acids that they contain, as described in Sections 8.2. The diets are designed by NIH Clinical center dietitians to be nutritionally complete. All foods will be provided by the NIH metabolic kitchen. Participants are required to visit the NIH Clinical Center each morning, Monday through Friday, to eat breakfast and to pick up study foods, and to return uneaten food to the kitchen. Participants are also asked to keep a daily log of food and beverage intake.

We will strive for 100% adherence to study diets and daily visit schedules, but recognize based on previous experience and reviews of literature that this may not be practical or achievable in an ambulatory setting for this length of time. Therefore, to maximize adherence participants are provided with a day of emergency meals to eat during missed days whenever possible. They will also receive group-specific food-based guidance from the nutrition team designed to mimic their diet group if they are unable to pick up study diets for more than one day. Subjects will record/report any non-study foods or beverages throughout the study and this will be analyzed as part of the study diet. Finally, we will measure adherence to study diets using two proxies: (1) the LA content of circulating plasma measured at baseline and 4, 8, and 12 weeks of diet exposure; and (2) the number of days they did not pick up study meals. In a posthoc/exploratory manner, we will test for effect modification of the diet effects based on adherence. If effect modification is evident, we will present the results of the adherent subgroup as a posthoc analysis.

Diet Phase

The sequence of procedures in the Diet Phase is given in Table 5. All time-points are targets, and may be adjusted based on practical considerations.

Table 5: Procedures during the Diet Phase

Diet Phase Testing Visits (12 week phase, Diet Days 1-84)

Procedure	Visit 1 (Day 28)	Visit 2 (Day 56)	Visit 3 (Day 84)
Blood draw	▲	▲	▲
Urine Pregnancy Test	▲	▲	▲
Mood Questionnaires	▲	▲	▲
Weight, Anthropometrics and Vital Signs	▲	▲	▲
DEXA Scan	▲	▲	▲
MRI Scan			▲
Muscle and Adipose Tissue Biopsies			▲
Buffet Meal Test	▲		▲

During the 12 week diet phase participants will visit the NIH outpatient metabolic unit every morning for breakfast (Monday-Friday). Each of these 60 meal visits will last about 20 minutes, for a total of 60 hours. Participants will complete the CPRS questionnaire after breakfast once every 2 weeks, which takes about 10 minutes to complete.

On 2 separate occasions after breakfast, once every 4 weeks on Days 28 and 56, participants will have a testing session lasting about 1.5 hours (Testing procedures are listed in Table 5). Twelve weeks after beginning the diet phase (Day 84), participants will have testing that lasts about 6 hours. They will have a shorter 2 hour testing session 4 and 8 weeks after beginning the diet phase.

Optional Continuation Phase

Those participants who were assigned to either diet “A” or diet “C” will have completed their participation after the 12-week diet phase of the study. Those who were assigned to diet “B” will be given the option of continuing a study diet for an additional 9 months (36 weeks).

The sequence of procedures in the Continuation Phase is given in Table 6. All time-points are targets, and may be adjusted based on practical considerations.

Table 6: Procedures during the Continuation Phase

Diet Continuation Testing Phase Visits (36 week phase, Diet Days 85-336)

Procedure	Visit 1 Day 126	Visit 2 Day 168	Visit 3 Day 210	Visit 4 Day 252	Visit 5 Day 294	Visit 6 Day 336
Blood draw	▲	▲	▲	▲	▲	▲
Urine Pregnancy Test		▲		▲		▲
Mood Questionnaires	▲	▲	▲	▲	▲	▲
Weight, Anthropometrics and Vital Signs	▲	▲	▲	▲	▲	▲
DEXA Scan		▲		▲		▲
MRI Scan						▲
Muscle and Adipose Tissue Biopsies						▲
Buffet Meal Test						▲

During the 36-week continuation phase, participants will continue to receive the study diet “B” that they received in the 12 week diet phase as shown in Appendix 1: Study Design Flow Diagram.

As in the main diet phase, participants will continue to visit the NIH outpatient metabolic unit every morning for about 20 minutes for breakfast (Monday-Friday). Each of these 180 visits will last about 20 minutes, for a total of 60 hours. Participants will fill out the CPRS questionnaire for about 10 minutes after breakfast once every 2 weeks.

On 5 separate occasions after breakfast, at 6, 12, 18, 24 and 30 weeks into the continuation phase, participants will have a testing session lasting about 1.5 hours. At 36 weeks into the continuation phase participants will have a testing session lasting about 6 hours (Testing procedures are listed in Table 6).

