7.6.3 Specimen collection for biomarker testing

Blood Collection

To assess the blood compositions of omega-6 and omega-3 fatty acids and their metabolic derivatives, fasting venous blood will be collected at 4 timepoints in the main study (Baseline Visit 3; Diet Phase Visits 1, 2 and 3). Blood will be collected from participants in the optional continuation phase at 6 additional time points (see Table 5: Continuation Phase Visits). Blood will be immediately processed and stored at -80 degrees C. See Table in Appendix 2 for a list of fatty acids and their metabolic mediators that will be assessed.

Genotyping

This project will collect DNA samples from the saliva of well phenotyped overweight subjects for genotyping. Genotyping will be performed on all study participants. Single gene mutations/polymorphisms of interest include: 1) those involved in fatty acid metabolism; 2) those implicated in the pathogenesis of obesity; 3) those implicated in the pathogenesis of medical and psychiatric conditions associated with obesity; 4) those linked to certain behavioral characteristics relevant to obesity and obesity-related comorbidities. On the consent form, participants can designate whether or not the DNA samples can also be stored for future research projects.

Muscle and adipose tissue biopsies and tissue procurement and post-biopsy pain assessment

Fat and muscle biopsies will be obtained before and after the dietary interventions, by the study physicians and/or nurse practitioner. In accordance with established NIDDK practices, biopsies will be performed on the Metabolic Unit or the adjacent 5SW day hospital, as described below.

Subcutaneous adipose tissue (3-5 g) will be removed from the abdominal region by aspiration with a 16-gauge needle under local anesthesia (e.g. 2% xylocaine).

Muscle biopsies (100-250 mg) will be obtained under local anesthesia from the vastus lateralis, as follows. The patient will be prepped and draped in sterile fashion. The muscle biopsy procedure involves numbing a nickel-sized portion of the skin of the thigh with a local anesthetic and making a small incision, approximately 1/4 inch. The biopsy needle is then inserted via the incision through adipose tissue and muscle fascia into the muscle. A small sample of muscle tissue is removed. The incision will then be closed with steri-strips and covered with a dressing. If the muscle is too deep to be reach, the muscle biopsy will not be attempted.

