7.6.4 Insulin Sensitivity

Homeostasis Model of Assessment – Insulin Resistance (HOMA-IR)

To assess insulin sensitivity, fasting blood glucose and insulin will be collected at each testing visit, for calculation of the HOMA-IR, a validated biomarker for estimating insulin sensitivity.

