7.6.5 Functional Satiety assessment

Ad-libitum Buffet Meal

Participants will be fed a standard breakfast meal containing 15% of energy needs (calculated using the Mifflin St. Joer equation with an activity factor of 1.5). Between the breakfast and buffet meal participants will be asked to fill out Visual Analogue Scales asking questions about hunger and satiety at 30-60 minute intervals. Six hours following the standard breakfast the patient will be placed in a food laboratory and presented with a buffet meal. They will be instructed to “eat until they are full.” The buffet meal will contain foods that will be weighed pre and post consumption in a metabolic kitchen so that the precise amounts of foods consumed can be calculated.

Buffet Meal Screening

Food Preference Questionnaire:

At screening patients will fill out a 50 item food preference questionnaire with buffet items embedded within it. If the patient reports dislike of $\geq 50\%$ of the food items on the buffet, they will be excluded from participation.

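### Section 7.5 schedules the Day 28, Day 56 and interim continuation blood draws after breakfast, against the fasting rules in 7.6.3 and 7.6.4, and its Day 28 session is too short for the buffet test

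*Combined protocol and SAP*

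**What the plan says.** **Timing of the sessions.** The overview paragraphs of 7.5 state: "Once every 4 weeks after breakfast, on Diet Day 28 and 56, they will have additional testing for about 1.5 hours". The Diet Phase part of 7.5 repeats this: "On 2 separate occasions after breakfast, once every 4 weeks on Days 28 and 56", and adds that "participants will have a testing session lasting about 1.5 hours (Testing procedures are listed in Table 5"). Table 5 marks a blood draw on Days 28, 56 and 84. Later in the same paragraph the session length changes: "They will have a shorter 2 hour testing session 4 and 8 weeks after beginning the diet phase".

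For the continuation phase, 7.5 places testing "On 5 separate occasions after breakfast, at 6, 12, 18, 24 and 30 weeks", at about 1.5 hours each, and Table 6 marks a blood draw at every visit. The overview paragraphs instead put testing after breakfast every 6 weeks, with no exception for week 36, and give 3 to 6 hours.

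**State of the blood.** Section 7.6.3 says "fasting venous blood will be collected at 4 timepoints in the main study" and names them as Baseline Visit 3 and Diet Phase Visits 1, 2 and 3. Its sentence on continuation blood does not repeat the word fasting. Section 7.6.4 says "fasting blood glucose and insulin will be collected at each testing visit", for HOMA-IR.

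**Buffet test.** Table 5 marks a buffet test on Day 28 and Day 84. Section 7.6.5 says "Six hours following the standard breakfast the patient will be placed in a food laboratory", with hunger and satiety ratings every 30 to 60 minutes in between.

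**The concern.** The protocol gives two incompatible instructions for the same blood sample. Staff who work from the visit schedule would draw fed blood; staff who work from the specimen section would draw fasting blood. Practice could also vary between visits or participants, and the plan does not ask for time since last intake, so the variation could not be identified afterwards.

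Four uses of the samples are exposed:

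- **Secondary Aim 1 (11.2)** compares rates of change across baseline and Days 28, 56 and 84. If the two middle points are fed and the first is fasting, part of any apparent change over time could be a change in meal state.
- **HOMA-IR (7.6.4)** is specified on fasting glucose and insulin. A fed sample does not meet that specification.
- **Plasma LA at weeks 4 and 8** is one of the two adherence proxies in 7.5 and feeds the post hoc adherent subgroup. A recent meal that contains LA could affect it.
- **The continuation series** contains Diet B only. With no concurrent control, a move from fasting to fed sampling could resemble a time trend.

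The buffet problem is separate. Under 7.1, Day 28 ends the iso-caloric phase, so this is the only on-diet buffet test before ad libitum eating begins. The stated session cannot hold it.

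**Working it through.** **Step 1. Prandial state, visit by visit.**

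| Visit | Timing in 7.5 | Fasting required by | Conflict |
|---|---|---|---|
| Baseline Visit 3 | not tied to breakfast | 7.6.3, 7.6.4 | none stated |
| Day 28 | after breakfast | 7.6.3, 7.6.4 | yes |
| Day 56 | after breakfast | 7.6.3, 7.6.4 | yes |
| Day 84 | not directly tied to breakfast | 7.6.3, 7.6.4 | not direct |
| Continuation weeks 6, 12, 18, 24, 30 | after breakfast | 7.6.4 only | yes, for glucose and insulin |
| Continuation week 36 | after breakfast in the overview; not in the continuation text | 7.6.4 only | depends on which text of 7.5 is used |

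Counts: 2 of the 4 time points in Secondary Aim 1. In continuation, 5 of 6 visits under the continuation text, or 6 of 6 under the overview.

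**Step 2. Does any other text settle the order of events?** No section says that blood is drawn on arrival, that breakfast is held back on test days, or that participants return later in the day. The note that time-points are targets lets visits move, but it does not say whether the blood is fasting or fed.

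**Step 3. Day 28 buffet, time needed against time available.**

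Inputs: interval from breakfast to buffet = 6 h (7.6.5); session after breakfast = 1.5 h or 2 h (7.5, Diet Phase).

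Shortfall = time needed − time available, with the buffet meal itself not counted:

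- 6 − 1.5 = 4.5 h
- 6 − 2 = 4 h

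The ratings show the same thing. Over 6 h (360 min), the 30 to 60 minute spacing gives 360/60 = 6 to 360/30 = 12 ratings. A 1.5 h session holds 1 (90/60, rounded down) to 3 (90/30). A 2 h session holds 2 (120/60) to 4 (120/30).

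The sessions of about 6 hours at Baseline Visit 3 and Day 84 are also tight. The buffet opens only at hour 6 after breakfast, and fasting blood would have to precede that breakfast.

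**Step 4. Session lengths that disagree within 7.5.** Days 28 and 56: 1.5 h against 2 h. Interim continuation visits: about 1.5 h against 3 to 6 h.

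**Step 5. Size of the meal effect.** It cannot be computed. The documents give no fed-versus-fasting difference for any analyte and no fatty-acid content for the breakfast.

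**The case against.** The strongest reply is that 7.6.3 and 7.6.4 are the procedure-specific sections and should govern, while 7.5 is an overview of visit lengths. Participants come in for breakfast each weekday, so drawing blood on arrival would be natural and would satisfy the fasting rule. That is plausible, and it means fed sampling is a risk rather than a certainty. It does not remove the conflict: 7.5 gives the after-breakfast timing in three places, points to tables that contain the blood draw, and nothing states which section prevails.

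Three stronger inferences are tempting, and the documents do not support them.

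- **That the error differs by arm and so biases the diet comparison.** Table 3 gives LA as 8 or 1 percent of daily food energy; the composition of breakfast is not given. For a buffet day, 7.6.5 specifies a standard breakfast without saying whether it is arm-specific. The primary fatty-acid outcome is plasma phospholipid composition (10.1), and nothing in the documents shows that one meal shifts it. An arm difference is possible but not established.
- **That the primary analysis is compromised.** Section 11.2 makes the 84-day measurement the outcome. The Diet Phase text ties the after-breakfast wording to Days 28 and 56 only. The overview sentence goes on to mention Day 84, but does not plainly carry the wording over.
- **That all continuation blood must be fasting.** Section 7.6.3 does not say so. The requirement rests on 7.6.4 and covers glucose and insulin.

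No comparable reply exists for the Day 28 buffet. Moving the visit date cannot fit a six-hour interval into two hours.

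**Conclusion.** The concern holds as an internal contradiction that should be corrected.

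- **Fasting state:** 7.5 conflicts with 7.6.3 and 7.6.4 at 2 of the 4 main-study blood time points. It conflicts with 7.6.4 at 5 or 6 of the 6 continuation visits, depending on which part of 7.5 is read.
- **Buffet:** the Day 28 session falls short by at least 4 to 4.5 hours.

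The consequences for Secondary Aim 1, HOMA-IR, the adherence marker and the continuation series are conditional on 7.5 being followed. Their size is unknown. The sample size is unaffected. Confidence is high for the contradiction and for the time arithmetic; it does not extend to any claim about the magnitude or direction of bias.

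**What to change.** 1. Amend all parts of 7.5 to agree with 7.6.3 and 7.6.4: blood at every testing visit, continuation included, is drawn fasting and before breakfast is served, as at baseline. State the same explicitly for continuation blood in 7.6.3.
2. Record hours since last intake at every draw.
3. Do not compute HOMA-IR from a non-fasting sample. Flag non-fasting samples for fatty acids and lipid mediators and run a sensitivity analysis without them. Deleting them outright could remove 2-AG and AEA values at two of four time points for an effect of unknown size.
4. Reconcile the Day 28 session length with 7.6.5, so that the buffet can be done with the same breakfast-to-buffet interval as at the tests it is compared with. Check the sessions of about 6 hours in the same way. Dropping the Day 28 buffet would also remove the conflict, but it would lose the only on-diet test before ad libitum eating.
5. Give one session length for Days 28 and 56 and one for the interim continuation visits, and state the order of events at week 36.

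Cost: items 1 to 3 and 5 need protocol wording, one recorded field and a change in the order of events at visits that already take place. Item 4 makes the Day 28 visit longer for participants and staff.
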